13.4 Handling of Missing Data and Subject Withdrawals

In general, unless otherwise stated missing data will not be imputed.

13.5 Investigator Post-Surgery Questionnaire

Any data from the Investigator Post- Surgery Questionnaire used to derive the efficacy endpoints described above will be entered into the Clinical Trial Database (CTDB) and included in line listings.

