
Eligibility Criteria
	
Inclusion:
 
 1. Male and Female subjects 18 years of age and older 2. Have a primary diagnosis, or a high clinical suspicion, of cancer in the lung warranting surgery based on CT/PET or other imaging 3. Are scheduled to undergo surgical thoracoscopy for diagnostic wedge resection followed by anatomic lung resection 4. Female subjects of childbearing potential or less than 2 years postmenopausal agree to use an acceptable form of contraception from the time of signing informed consent until 30 days after study completion 5. Ability to understand the requirements of the study, provide written informed consent and authorization of use and disclosure of protected health information, and agree to abide by the study restrictions and to return for the required assessments 
Exclusion:
 
 1. Previous exposure to OTL38 2. Any medical condition that in the opinion of the investigators could potentially jeopardize the safety of the subject 3. History of anaphylactic reactions to folate, including synthetic folic acid (pteroylmonoglutamic acid) and contrast agents containing indocyanine green for near infrared imaging. Subjects with a medical history of ‘idiopathic anaphylaxis’ will require evaluation. 4. History of allergy to any of the components of OTL38, including folic acid 5. A positive serum pregnancy test at Screening or a positive urine pregnancy test on the day of surgery or day of admission for female subjects of childbearing potential 6. Clinically significant abnormalities on electrocardiogram (ECG) at screening. 7. Presence of any psychological, familial, sociological condition or geographical challenges potentially hampering compliance with the study protocol and follow-up schedule 8. Impaired renal function defined as eGFR < 50 mL/min/1.73m² 9. Impaired liver function defined as values > 3x the upper limit of normal (ULN) for alanine aminotransferase (ALT) or aspartate aminotransferase (AST), alkaline phosphatase (ALP), or >2x ULN for total bilirubin except in subjects with Gilbert’s syndrome. 10. Received an investigational agent in another investigational drug or vaccine trial within 30 days prior to the administration of study drug 11. Known sensitivity to fluorescent light

Number of Subjects
	
Up to approximately 130 subjects

Number of Investigator Sites
	
Up to approximately 15 investigational sites

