Statistical Methods	
The primary analysis of the CSE primary efficacy endpoint will be a one-sample test for a proportion via an exact binomial test conducted at the two-tailed alpha level of 0.05. [REDACTED]
 
[REDACTED]
 
[REDACTED]
 
[REDACTED]
 
[REDACTED]
 
Analysis of Secondary Efficacy Endpoints
 
The sensitivity endpoints described above will be analyzed [REDACTED]
 
[REDACTED]
 
[REDACTED]
 
[REDACTED]
 
[REDACTED]

Safety	
Safety will be described via subject incidence of treatment emergent adverse events (TEAEs) including serious TEAEs as well as adverse device effects (ADEs). Additionally, summary statistics and/or shift tables will be provided for vital signs, physical exams, ECGs, and laboratory parameters at baseline and post-baseline measurements. All subjects exposed to OTL38 and/or the imaging system will be evaluated for safety and be included in the Safety Analysis Set.

Table of Contents

1 PROTOCOL SYNOPSIS.....4

2 SCHEDULE OF ASSESSMENTS.....14

3 BACKGROUND INFORMATION.....20

3.1 Background.....20

3.2 Rationale.....21

3.3 Investigational Product.....22

3.3.1 Prior Clinical Experience.....22

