3.4.2 Benefits

The potential benefits of OTL38 for lung nodule and lesion imaging are:

- Localization of the primary nodule seen on CT/PET
- Increasing the possibility of complete removal of primary nodules and/or cancer without compromising healthy tissue
- Removal of additional lesions not previously noted on CT/PET
- Identification of cancer positive margins of excised tumors
- Reducing the occurrence of positive resection margins
- Improved staging of the tumor.
- Potentially improving overall survival rates

All three CSE components are individually sufficient to identify a clinical benefit as the surgeon would not have been able to identify the CSE by white light and/or palpation alone. Although the use of OTL38 is not intended to change the surgeon's opinion to remove additional tissue based on experience, visualization, or tactile senses, the identification of cancerous lesions identified with NIR alone can lead to improved resection of the cancer and better surgical outcomes.

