5.8.3 Investigator Post-Surgery Questionnaire (Visit 2b)

After each surgery, the Investigator will fill out the questionnaire located within the study reference manual at the conclusion of each case.

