5.8.5 Camera/Imaging System Exposure (NIR Fluorescent Imaging Group Only)

A camera/imaging system will be used to identify tumor lesions under fluorescence prior to surgical excision of lesions, and again after surgical excision of lesions to identify persistent lesions. The Investigator will record the start and stop time for each in situ exposure to fluorescence imaging (pre-resection, post-initial resection, other [give reason]) in the eCRF. The total time of fluorescence will be calculated automatically.

Back table imaging will not be included in the fluorescence exposure time.

Status	Time On Fluorescent Light	Time Off Fluorescent Light
Before surgical excision		
After initial surgical excision		
Other (explain reason)		

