5 TREATMENT ASSIGNMENT

It is anticipated that all participating subjects will receive OTL38.

Randomized group assignment will be blinded until revealed for an individual subject. Once revealed, the randomized group assignment for an individual subject will no longer be blinded.

Subjects receiving OTL38 and randomized to

Further information regarding the randomization process will be detailed in a separate document.

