12.1 Primary Efficacy Endpoint

The primary efficacy endpoint is the proportion of FAS subjects who have a CSE. [REDACTED]

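### Does SAP 13.5 let hindsight into the primary CSE proportion through the surgeon's end-of-case questionnaire?

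*SAP*

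**What the plan says.** The primary endpoint is stated in SAP 12.1: "The primary efficacy endpoint is the proportion of FAS subjects who have a CSE". The Protocol synopsis (Statistical Methods) tests it with "a one-sample test for a proportion via an exact binomial test conducted at the two-tailed alpha level of 0.05". The synopsis gives the planned size as "Up to approximately 130 subjects". The null value, the assumed CSE rate and the size of the Full Analysis Set (FAS) are redacted.

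The questionnaire appears in two places. Protocol 5.8.3 says: "After each surgery, the Investigator will fill out the questionnaire located within the study reference manual at the conclusion of each case". SAP 13.5 concerns "Any data from the Investigator Post- Surgery Questionnaire used to derive the efficacy endpoints described above" and says that such data go into the clinical trial database and the line listings. That one sentence is the whole of SAP 13.5.

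Three other places bear on timing and meaning:

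- SAP 5 keeps the group assignment blinded until it is revealed for the individual subject. It then adds: "Once revealed, the randomized group assignment for an individual subject will no longer be blinded".
- Protocol 5.8.5 says: "A camera/imaging system will be used to identify tumor lesions under fluorescence prior to surgical excision of lesions". Imaging is repeated after excision.
- Protocol 3.4.2 explains the benefit of a CSE by saying that "the surgeon would not have been able to identify the CSE by white light and/or palpation alone".

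**The concern.** Protocol 3.4.2 presents a CSE as something the surgeon could not have found without fluorescence. That is a counterfactual judgement. If it is made at the end of the case, by the person who has just seen the fluorescence, it is open to hindsight. SAP 13.5 contemplates that questionnaire answers may feed efficacy endpoints, and nothing visible excludes the CSE from those endpoints.

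The form of the test raises the stakes. In a comparison of two arms, mislabelling common to both would partly cancel. In a one-sample test against a fixed proportion it does not: each subject wrongly counted as a CSE adds to the tested count. The sensitivity analysis of the primary endpoint in SAP 13.1.1 is described as descriptive summaries, so the visible text offers no formal retest without questionnaire-dependent events.

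**Working it through.** **1. What the documents establish about the link.** Three statements have to hold together for the primary test to be exposed.

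| Statement | Visible support |
|---|---|
| The form is completed after NIR, by an unblinded investigator | Yes, for imaged subjects: Protocol 5.8.3 and 5.8.5, SAP 5 |
| The form asks what would have been found without NIR | None. The form is in the study reference manual, which is not among the documents |
| The CSE is derived from that answer | None. SAP 13.5 is conditional, and the endpoints it refers back to are primary, secondary and exploratory |

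The text that would settle the third row is redacted: the CSE components (Protocol 6.1, SAP 12.1), the Day 1 surgery steps (Protocol 5.8.1.2), the surgical reporting schematics (Protocol 5.8.2) and the primary analysis (Protocol 8.2.5.1, SAP 13.1). Redacted text cannot be counted as absent. Two visible features are compatible with a record made before NIR: the assignment is blinded until it is revealed for each subject (SAP 5), and all excised lesions go to tissue processing (Protocol 5.8.4). Neither proves that such a record exists.

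**2. How much it would matter if the link existed.** The planned number cannot be reproduced, because its inputs are redacted. The following is an illustration with an assumed sample size n and null p0.

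Let e be the share of true non-events relabelled as CSE. When the true rate equals p0, the observed rate is

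q = p0 + (1 − p0) × e.

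The upper-tail error is P(X ≥ c), where X is binomial(n, q) and c is the smallest count that rejects. With p0 = 0.10 and e = 0.03, q = 0.10 + 0.90 × 0.03 = 0.127. In 110 subjects that is 110 × 0.90 × 0.03 = 3.0 extra events expected.

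Results for n = 110, with c chosen so that the upper tail is at most 2.5%:

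| p0 | c | e = 0 | e = 3% | e = 5% |
|---|---|---|---|---|
| 10% | 19 | 1.3% | 10.1% | 24.0% |
| 15% | 25 | 2.0% | 9.9% | 20.8% |
| 20% | 31 | 2.5% | 9.2% | 17.9% |

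The visible text does not say which two-sided exact test is meant. Under the minimum-likelihood version the cutoff at p0 = 10% is 18, and the first row becomes 2.5%, 15.6% and 32.8%. The other two rows do not change. For n = 90, 110 and 130 and nulls of 10% to 20%, e = 3% gives about 6% to 15% with equal tails and 9% to 16% with minimum likelihood.

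**3. Direction.** These figures allow only upward error. A surgeon looking back may also answer that the lesion would have been found anyway, which removes a CSE. If a share d of true events is lost in that way,

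q = p0 × (1 − d) + (1 − p0) × e.

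The two errors cancel when d = (1 − p0) × e / p0. For p0 = 0.10 and e = 0.03 that is 0.90 × 0.03 / 0.10 = 0.27. At a rate this low it takes a large downward share to offset a small upward one, so net inflation is the more natural fear. It is still not the only possible direction, and the documents give neither e nor d.

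**The case for a change.** The strongest argument for a change rests on unredacted text. The sentence in SAP 13.5 is complete as it stands, and it says neither which items and endpoints are meant nor which source prevails if the questionnaire and an intraoperative record disagree. A pre-NIR record elsewhere would not by itself settle that precedence. Naming the source would take a sentence, and repeating the same exact test without questionnaire-dependent events would cost almost nothing.

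Part of this stands. The items are not named, the form is completed after the fact in an open-label study, and a one-sample test is fragile to upward mislabelling. But the sentence governs what is entered and listed; it is not a scoring rule for the CSE. Precedence between sources belongs with the endpoint derivation, and that is the redacted text. Protocol 3.4.2 gives a rationale for benefit and does not instruct anyone how to score an event. Nor does SAP 13.5 say that the remaining questionnaire items will be kept out of the database. The proposed retest would alter nothing unless some CSE really does depend on a questionnaire answer, and no visible text says that one does.

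**Conclusion.** No change to the plan follows. The visible documents do not show that the primary CSE uses the questionnaire, that the questionnaire asks a retrospective counterfactual, or that findings before NIR go unrecorded. The safeguard one would ask for may already be the procedure in the redacted surgical steps. What is left is a missing detail: which questionnaire items, if any, feed the CSE, and whether white-light and palpation findings recorded before NIR take precedence. The sponsor can answer that from the unredacted plan, and an analyst working from it would have the derivation at hand.

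If the link did exist, the effect would not be trivial. With 110 subjects, nulls of 10% to 20% and 3% one-way relabelling, an upper-tail error of at most about 2.5% would become roughly 9% to 16%, depending on the null and the version of the exact test. The sample size, the null, the relabelling rate and the one-way direction are all assumptions, so these figures measure fragility; they are not a finding about this trial.

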14 SAFETY EVALUATIONS

14.1 Overview of Safety Analysis Methods

Safety will be evaluated using the safety analysis set and will include treatment emergent adverse events (TEAEs), adverse device effects (ADEs), serious adverse events (SAEs), vital signs, physical examinations, clinical laboratory measurements, electrocardiograms, and concomitant medications.

In general, the analysis of safety will be descriptive. No data will be imputed except for partial dates if required to determine if an adverse event is treatment emergent or a medication concomitant with exposure to study drug.

As noted above, the baseline value used for the analysis will be considered the last non-missing value recorded for a particular safety parameter before exposure to study drug. However, where relevant, a change from screening to pre-infusion will also be included in the presentations.

14.1.1 Imputation of Partial Adverse Event Dates

Figure 1 consists of five horizontal bar charts, each representing a different type of cancer. The y-axis for all charts is labeled 'Percentage of patients' and ranges from 0 to 100. The x-axis for all charts is labeled 'Number of patients' and ranges from 0 to 1000. The treatments shown are: Radiotherapy (RT), Chemotherapy (CT), Radiation Therapy (RT), Chemotherapy (CT), and Radiation Therapy (RT). The bars are black with white outlines. The data for each chart is as follows:

Cancer Type	RT (%)	CT (%)	RT (%)	CT (%)	RT (%)
1	100	100	100	100	100
2	100	100	100	100	100
3	100	100	100	100	100
4	100	100	100	100	100
5	100	100	100	100	100

14.2 Extent of Exposure

Study drug will be administered as a single infusion. A summary of the number of subjects exposed to study drug and any subjects not receiving their full dose will be described.

14.3 Adverse Events

Adverse events that are not treatment-emergent, those occurring after signing the ICF but prior to exposure to OTL38 administration, will be provided in line listings. Treatment emergent adverse events (TEAEs) will be summarized via the Medical Dictionary for Regulatory Activities (MedDRA) system organ class and preferred term using subject incidence rates. Data will be tabulated by severity, physician assessment of relationship to study drug, serious TEAEs, and TEAEs leading to death or early study withdrawal. Further description of TEAEs may be defined by temporal onset to study drug infusion and/or by event incidence. Additional summaries of TEAEs identified as potential ADEs will also be provided for those subjects exposed to imaging.

Treatment-emergent AEs will be summarized for all subjects in the Safety Analysis Set (SfAS). Summary tables will reflect the number and percent of subjects experiencing at least 1 TEAE in each system organ class and preferred term. The overall number and percent of subjects

experiencing any treatment-emergent AE will also be provided. All percentages will use the number of subjects in the SfAS set as the denominator. An exception will be the presentation of ADEs which will use all subjects undergoing fluorescent light imaging as the denominator. If a subject has more than one AE within a system organ class, the subject will be counted only once in that system organ class. If a subject has more than 1 AE that codes to the same preferred term, the subject will be counted only once for that preferred term.

Treatment-emergent AEs will also be summarized by the maximum relationship to study drug as determined by the Principal Investigator as well as the maximum severity of the event. Relationship to study drug will be scored as Related, Possibly Related, or Not Related. Related AEs will be classified as those scored as Related or Possibly Related. Severity will be rated as per CTCAE v5.0:

- Grade 1 Mild; asymptomatic or mild symptoms; clinical or diagnostic observations only; intervention not indicated.
- Grade 2 Moderate; minimal, local or noninvasive intervention indicated.
- Grade 3 Severe or medically significant but not immediately life-threatening; hospitalization or prolongation of hospitalization indicated; disabling;
- Grade 4 Life-threatening consequences; urgent intervention indicated.
- Grade 5 Death related to AE

If a subject experiences more than 1 AE within system organ class or preferred term, that subject will be counted only once for that event under the maximum severity or most related category within the relevant category. In the event that the relationship to study drug or the severity of the event is missing, for tabulation purposes the maximum relationship will be assumed, and a Grade 3 (Severe) level of severity will be assumed.

Adverse Events of Special Interest (AESIs) will be captured and analyzed. An AESI is defined as an infusion related reaction and will be identified through the following mechanisms to include all AEs that meet the following criteria:

- AE that are not considered procedural in nature (Procedural complications and administration related problems will be excluded and defined as any AE with a preferred term of “procedural complication” or “infusion site discomfort” will be excluded.)

AND meets at least one of the following:

- AE that resulted in interruption of study drug infusion in the study drug administration data (study drug administration CRF; was infusion interrupted = yes; reason for interruption = AE)
- AE that resulted in study drug interruption or study drug withdrawal in the AE data (all AEs with an action taken with study drug = drug interrupted, or drug withdrawn)
- AE that started during the study drug infusion as per the recoded start time (AEs with a start date of Study Day 1 AND a start TIME within the infusion window as defined as start time >

infusion start time and \leq infusion stop time; AEs that have the same start time as the study drug infusion will not be counted)

- AE presumed to start during the study drug infusion as per the recorded start/stop dates and assigned relatedness (AEs without a recorded start time, that have both a start date and stop date of Study Day 1, and are indicated as Related or Possibly Related for their relationship to OTL38 Infusion)
- AE that started during the study drug infusion as per the recorded start time which abated after infusion being stopped or reduced.

Incidence of TEAEs will be summarized by age group, race, and gender if there are sufficient numbers of subjects within these subgroups. Otherwise only line listings will be provided.

All AEs will be presented in data listings for subjects. If required, the line listings will distinguish between adverse events occurring after signing the ICF but prior to exposure to study drug, and TEAEs. If a partial date was imputed, the line listings will include both the observed and imputed date. Imputations for missing relationships and severities of AEs will not be included in the line listings.

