8.2.5.2 Secondary Efficacy Endpoints

- Sensitivity and False Positive Rate (FPR)

[REDACTED]

[REDACTED]

[REDACTED]

- [REDACTED]

[REDACTED]

8.2.5.3 *Exploratory Efficacy Endpoints*

In general, exploratory efficacy endpoints will be descriptive.

8.2.5.4 *Safety Evaluations*

Safety will be evaluated using the Safety Analysis Set and will include treatment emergent adverse events (TEAEs), adverse device effects (ADEs), serious adverse events (SAEs), vital signs, physical examinations, clinical laboratory measurements, electrocardiograms, and concomitant medications. Treatment emergent adverse events are adverse events occurring during or after study drug exposure. Adverse device effects occur during or after exposure to the imaging device and classified as device effects by the Investigator. In general, the analysis of safety will be descriptive. No data will be imputed except for partial dates if required to determine if a medical event is a TEAE or a medication concomitant with exposure to study drug.

In general, the baseline value will be considered the last non-missing value recorded for a particular safety parameter before exposure to study drug. Where relevant, changes from baseline summaries will also include the change from screening to pre-infusion.

8.2.5.4.1 *Adverse Events and Adverse Device Effects*

For subjects in the Safety Analysis Set, medical events occurring after the signing of informed consent but prior to exposure to OTL38 administration will be considered a study AE, but not a treatment emergent AE (TEAE). It is anticipated that study AEs will be sparse and presented in line listings. Treatment emergent adverse events (TEAEs) will be summarized via the MedDRA system organ class and preferred term using subject incidence rates. Data will be tabulated by severity, physician assessment of the relationship to study drug, serious TEAEs, and TEAEs leading to death or study withdrawal. Further description of TEAEs may be defined by temporal onset to study drug infusion. Additional summaries of TEAEs identified as ADEs will also be provided.

8.2.5.4.2 *Clinical Laboratory Evaluations*

The analysis of laboratory parameters will include descriptive statistics for the change from baseline to each post-baseline study visit as well as shifts from baseline to each post-baseline study visit for categorical lab parameters.

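### SAP 14.3 tabulates any ungraded TEAE as Grade 3, even one recorded as fatal or life-threatening, and its wording conflicts with the dates-only imputation rule in SAP 14.1 and Protocol 8.2.5.4

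*SAP*

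**What the plan says.** SAP 14.3 summarizes TEAEs by maximum severity and maximum relationship to study drug, on CTCAE v5.0. Three of its grades matter here: "Grade 3 Severe or medically significant but not immediately life-threatening", "Grade 4 Life-threatening consequences; urgent intervention indicated" and "Grade 5 Death related to AE".

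The missing-value rule comes shortly after the scale. Its trigger is "In the event that the relationship to study drug or the severity of the event is missing", and its consequence is that "for tabulation purposes the maximum relationship will be assumed, and a Grade 3 (Severe) level of severity will be assumed". The section later adds: "Imputations for missing relationships and severities of AEs will not be included in the line listings".

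SAP 14.1, the overview of safety methods, states: "No data will be imputed except for partial dates if required to determine if an adverse event is treatment emergent". The only other exception there covers dates needed to classify a medication as concomitant. Protocol 8.2.5.4 has the same rule: "No data will be imputed except for partial dates if required to determine if a medical event is a TEAE".

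SAP 14.4 separately tabulates and lists serious TEAEs and TEAEs resulting in death. Protocol 7.5 obliges the investigator to assign a severity to every AE, on four levels that end at life-threatening and include no level for death.

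**The concern.** Two things look wrong.

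First, the severity default depends only on the grade being absent. It ignores what else is recorded about the event. A TEAE that ended in death, or that met the life-threatening criterion for seriousness, would be counted in a category whose definition excludes immediate threat to life. The same event would appear in the SAP 14.4 tables as a death or an SAE, so two tables in one report would disagree about it. The two halves of the rule are also unequal: relationship goes to the top of its scale, severity does not.

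Second, one section of the SAP limits imputation to partial dates, and another imputes relationship and severity and calls the result imputation.

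At stake is agreement among the safety tables for the few most serious events, and having the grading of an ungraded death settled before the data are seen.

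**Working it through.** The plan gives no figure to reproduce. The check is mainly a comparison of texts, with a little arithmetic to show scale.

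**1. Does the Grade 3 rule have an exception?** The trigger in SAP 14.3 names a missing relationship or a missing severity and nothing else. Neither outcome nor seriousness is mentioned. A fatal or life-threatening TEAE without a grade therefore falls under it.

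**2. Does Grade 3 contradict such an event?** Yes. By the SAP's own definitions a life-threatening event belongs in Grade 4, a death in Grade 5, and Grade 3 rules out immediate threat to life.

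**3. Do the imputation rules conflict?** SAP 14.1 and Protocol 8.2.5.4 except partial dates only. SAP 14.3 assigns two other items and labels them imputations. A let-out for rules stated elsewhere appears in SAP 13.4, within the efficacy methods, and in Protocol 8.2.5.7. It is absent from the two safety sentences. The qualifier at the start of that paragraph in SAP 14.1 belongs to the preceding sentence, on descriptive analysis. The conflict is literal.

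**4. Is the rule applied item by item?** The trigger joins the two items with *or*, and the consequence then assigns both. Item-by-item imputation is probably meant, but the text does not say so.

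**5. How many subjects could be affected?** Inputs: up to about 130 subjects (Protocol synopsis), all assumed to be in the safety set; the phase 2 lung study of 100 subjects (Protocol 3.3.5), with Grades 1 to 4 in 24, 41, 25 and 4 subjects and no deaths.

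- Expected Grade 4 subjects: 0.04 × 130 = 5.2, about 5, plus any deaths.
- Shift per subject wrongly placed in Grade 3: 1/130 = 0.77 percentage points.
- The documents give no rate of missing severity. Across the whole range, from none to all 5 of these subjects, the shift runs from 0 to 5/130 = 3.8 percentage points. The upper end would require every such subject to be ungraded.
- SAP 14.3 counts a subject once per row, at maximum severity. A subject with another Grade 4 or 5 event in that row does not move.

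**6. Which way does the default err overall?** The phase 2 grades sum to 24 + 41 + 25 + 4 = 94, which equals the number of subjects with a TEAE. Assume that missingness is unrelated to grade:

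| True grade | Subjects | Effect of assigning Grade 3 |
|---|---|---|
| 1 or 2 | 24 + 41 = 65 (65/94 = 69%) | overstated |
| 3 | 25 (25/94 = 27%) | correct |
| 4 | 4 (4/94 = 4%) | understated |

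The default is conservative for most events and errs the other way only at Grades 4 and 5.

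**The case against.** The strongest case on the other side is that this is editorial. Grading is mandatory under Protocol 7.5, and an ungraded fatal or life-threatening event would also have to survive 24-hour SAE reporting. The default overstates severity more often than it understates it, and the plan nowhere promises a worst-case rule. The rule serves tabulation only, and the imputed values stay out of the listings. All of this stands and limits the weight of the point. It does not remove it, because the rule as written gives a wrong grade in the cases where the database already holds the contrary information.

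A reader might infer more than the documents support:

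- *That deaths or SAEs would be hidden.* SAP 14.4 tabulates and lists them without reference to grade. At most, the severity tables carry too low a grade.
- *That every SAE subject is exposed to the error.* The phase 2 SAE rate of 14% would give 0.14 × 130 = 18.2 subjects. But Protocol 7.1 counts hospitalization as serious, and SAP 14.3 places hospitalization in Grade 3. For such events the default is already right.
- *That the count of related TEAEs depends on which rule a programmer picks.* SAP 14.1 is a general statement. SAP 14.3 is a specific instruction, and it goes on to say how its imputations are handled in listings. In practice there is one operative rule, and 14.1 simply fails to name it.

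The objection also exposes a trap in the obvious repair. If sites grade on the four levels of Protocol 7.5, a graded fatal event can never reach Grade 5, while an ungraded one would be moved there. That mismatch has to be settled together with the default.

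**Conclusion.** The point holds as a small, definite defect. Followed literally, SAP 14.3 puts an ungraded fatal or life-threatening TEAE in a grade that the SAP defines as something else, and the severity table can then disagree with SAP 14.4. The wording conflict with SAP 14.1 and Protocol 8.2.5.4 is certain; its practical effect is slight.

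The size is at most 0.8 percentage points per affected subject in any row, among about 5 subjects plus any deaths. This rests on 130 subjects in the safety set and on the phase 2 Grade 4 rate carrying over; it is an illustration of scale, not a forecast. The frequency of missing grades is unknown and should be low. The eCRF is not among the documents, so which severity scale sites actually enter is also unknown.

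The documents do not support a claim that the safety reporting as a whole understates serious events. The change is still worth making before analysis, because a decision on how to grade a death is hard to defend once the data have been seen.

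**What to change.** **SAP 14.3.** State that only the missing item is imputed, so that a missing relationship never alters a recorded grade. For missing severity, tabulate as Grade 5 if the recorded outcome is death, as Grade 4 if the life-threatening seriousness criterion is recorded, and otherwise as Grade 3.

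**SAP 14.1.** Name missing AE relationship and severity as exceptions beside partial dates, and record in the SAP that this departs from Protocol 8.2.5.4.

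**Severity scale.** Reconcile the four levels of Protocol 7.5 with the five CTCAE grades of SAP 14.3, and say how a fatal event is tabulated when the investigator did enter a severity, so that graded and ungraded deaths are treated alike.

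**Cost.** A few sentences in the SAP and a little programming. Death and SAE status are already needed for SAP 14.4; that the life-threatening criterion is held as a separate field is an assumption to confirm against the eCRF. The severity table may look slightly less favourable. Documenting the departure in the SAP should avoid a protocol amendment for the imputation rule alone; reconciling the scales may need a protocol clarification if the Protocol 7.5 wording is the part that changes.
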